4 TRIAL DESIGN

The trial is a cluster randomised trial (CRT), where the research sites are randomised to one or other intervention. The intervention will become the standard of care at the research site and will be given to all participants unless there is a contraindication to the intervention (or an indication for the alternative intervention).

The CHELsea II trial (definitive trial) leads on from the CHELsea I trial (feasibility trial) [8,9]: the feasibility trial was conducted to ensure that the definitive trial “could be done”. The CHELsea I trial achieved all of the pre-determined criteria for success [9], and so there is no rationale for major amendments to the trial protocol (i.e., trial design, trial methods).

Score	Term	Description
+4	Combative	Overtly combative, violent, and immediate danger to staff
+3	Very agitated	Pulls or removes tube(s) or catheter(s) and aggressive
+2	Agitated	Frequent non purposeful movements
+1	Restless	Anxious or apprehensive but movements not aggressive or vigorous. Frequent movements, nonaggressive, in patient who is not fully alert
0	Alert or calm	
-1	Drowsy	Not fully alert but has sustained (more than 10 seconds) awakening, with eye contact to voice
-2	Light sedation	Briefly (less than 10 seconds) awakens with eye contact to voice
-3	Moderate sedation	Any movement (but not eye contact) to voice
-4	Deep sedation	No response to voice but any movement to physical stimulation
-5	Unarousable	No response to voice or physical stimulation

Table 2 – Modified Richmond Agitation Sedation Scale (m-RASS) [27].

We considered undertaking a “conventional” randomised controlled trial (RCT). However, RCTs are problematic in palliative care, and especially in end-of-life care [29]. Indeed, there have only been three published RCTs of CAH, and these studies recruited very small numbers of participants (i.e., 222 participants in total) [10-12]. Moreover, the principal RCT of CAH failed to meet its target for recruitment [12]. Hence, after reviewing the literature, we decided to undertake a cluster randomised trial [30,31].

CRTs are well established within palliative care [32,33], and specifically within end-of-life care [34-37] (and many other areas of medicine [30]). For example, Zimmermann et al performed a CRT of “early palliative care” in patients with advanced cancer: they “opted for cluster rather than individual randomisation...on the basis of evidence from the health services literature and advice from oncologists that it is difficult to recruit patients to be individually randomised (or not) to an intervention such as palliative care, in view of strong preconceived preferences among patients and their oncologists” [33]. A similar argument exists for CAH.

5 TRIAL SETTING

Research sites (80 in total) will be either NHS hospitals, or NHS/voluntary hospices in the four countries of the United Kingdom (i.e., England, Wales, Scotland or Northern Ireland). NHS hospitals will need to have a specialist palliative care team, and ideally either a palliative care unit or designated palliative care beds: they will need a relevant clinician willing to be the PI, and this person should ideally have experience in undertaking relevant research. NHS/voluntary hospices will need to have an inpatient unit: they will need a relevant clinician willing to be the PI, and this person should ideally have experience in undertaking similar research.

6 PARTICIPANT ELIGIBILITY CRITERIA

The target population is all patients in the last days of life that are inpatients in the research sites, and that meet the inclusion/exclusion criteria for the trial (see below).

6.1 Inclusion criteria

The inclusion criteria are:

- a) any sex
- b) age \geq 18 years
- c) estimated prognosis of \leq 1 week. [Clinical opinion - MDT].
- d) patient unable to maintain sufficient oral fluid intake (i.e., $< 1\text{L/day}$).

6.2 Exclusion criteria

The exclusion criteria are:

- a) patient is dehydrated (guidance on indicators of dehydration in Appendix 5)
- b) patient has a relevant Advance Directive to Refuse Treatment (ADRT)
- c) clinical indication for CAH
- d) clinical contraindication to CAH
- e) contraindication to cannulation
- f) total parenteral nutrition/enteral feeding in situ
- g) patient has had delirium in last 24 hours
- h) patient has had audible upper airway secretions in last 24 hours
- i) patient likely to be transferred elsewhere for end-of-life care
- j) patient has clinically significant cardiac failure as deemed by clinical team (see criteria "d")

- k) patient has clinically significant renal failure as deemed by clinical team (see criteria "d")
- l) patient has clinically significant dementia as deemed by clinical team (potential false positives on delirium screening)

Patients that are dehydrated will be eligible for inclusion after correction of dehydration has occurred.

Patients in research sites that are randomised to Standard intervention B, who are already receiving CAH, are eligible to take part in the trial (assuming they meet the other inclusion criteria). However, ongoing CAH must be given as per the protocol

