2 RATIONALE

As discussed, the provision of CAH at the end-of-life is one of the most contentious issues in medicine. The “issue” is not new [18], and the debate primarily continues due to the lack of evidence for/against CAH [3,4]. Recently, the “issue” has received greater attention due to the widespread negative publicity about the Liverpool Care Pathway (LCP), and the subsequent Neuberger review of the LCP (which resulted in withdrawal of the LCP in the UK) [2].

The Neuberger review noted that “most of the submissions to the Review from relatives and carers that were critical of the LCP made reference to hydration and nutrition” [2]. Moreover, the Neuberger review comments that “if fluids are stopped without review over many days, death from dehydration will be inevitable, the lack of hydration having accelerated the dying process” [2]. It should be noted that the Neuberger review also highlighted concerns about the use of sedative drugs at the end-of-life (see above).

Data from recent national audits of end-of-life care in hospitals in the UK suggests that there has been an increase in the number of patients receiving CAH in the last days of life [19,20]. Thus, 29% patients were receiving CAH “at the time of the patient’s death” in 2013, whilst 43% patients were receiving CAH “in the last 24 hours before the patient’s death” in 2016 [20]. This major change in practice does not relate to any new evidence (or, indeed, any new guidance), and undoubtedly reflects the widespread negative publicity around the LCP, and specifically the negative publicity around withholding/withdrawing CAH at the end-of-life [2].

In terms of guidance, the NICE guideline on care of dying adults in the last days of life states that healthcare professionals should “discuss the risks and benefits of clinically assisted hydration with the dying person and those important to them” [21]. However, the NICE guideline highlights the lack of evidence on CAH (in order to do so): “clinically assisted hydration may relieve distressing symptoms or signs related to dehydration but may cause other problems”; “it is uncertain if giving clinically assisted hydration will prolong life or extend the dying process”; “it is uncertain if not giving clinically assisted hydration will hasten death” [21].

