7 TRIAL PROCEDURES

7.1 Recruitment

Participants will be inpatients at the trial sites and will need to meet all of the inclusion criteria, and not meet any of the exclusion criteria of the trial (see above). [All patients that meet the inclusion/exclusion criteria for the trial will be eligible for the trial].

The clinical team will identify suitable patients as part of routine clinical practice, and the research team will then approach the patient, personal consultee or nominated consultee (as appropriate) to see whether they want to take part in the trial.

Each trial site will have a screening log, which records anonymised personal data for all screened patients (i.e., initials and date of birth), this information will be obtained from the patient's medical records. Information will also be recorded about reasons for non-participation, e.g., patient ineligible (reason stated), patient declined, personal / nominated consultee declined, other reason (reason stated): this information will be provided by the clinical team / research team (as appropriate).

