7.3.1 Method of implementing the randomisation/allocation sequence

A sampling frame containing all approved sites, categorised by type of unit and home country will be drawn up, and each unit matched to an allocation from the independently prepared randomisation list by the Trial Statistician. This process will ensure there can be no allocation bias.

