7.4 Blinding

The trial is unblinded (to participants and researchers).

[figure not shown]

Figure 2 – Consent flow chart.

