7.5 Baseline data

Baseline data will be collected to describe the trial population (so that comparisons can be made with other populations):

- a) Age
- b) Sex – female, male

- c) Ethnicity
- d) Primary diagnosis – cancer, non-malignant (with specific diagnosis)
- e) Site of care – hospital, hospice
- f) Home-country – England, Northern Ireland, Scotland, Wales
- g) Type of consent – participant, personal consultee, nominated consultee

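### Eligibility of patients already receiving CAH is stated only for intervention B sites, and no entry record of prior CAH or Nu-DESC is planned against which the arms could be compared

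*Protocol*

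**What the plan says.** **Eligibility.** Protocol section 6.2 gives one list of exclusions for the whole trial and then adds a sentence tied to the allocated arm: "Patients in research sites that are randomised to Standard intervention B, who are already receiving CAH, are eligible to take part in the trial". The sentence is conditional on the remaining inclusion criteria, and continuing fluids must follow the protocol regimen. Nothing parallel is written for intervention A sites. No exclusion names current CAH as such. The nearest is (c), "clinical indication for CAH". Section 7.1 adds: "All patients that meet the inclusion/exclusion criteria for the trial will be eligible for the trial".

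**Who selects, and when.** Under section 7.1 the clinical team identifies patients and the research team approaches them. Section 8 makes the allocated intervention the site's usual care while the trial runs. Section 7.4 states: "The trial is unblinded (to participants and researchers". Of the matching of sites to the randomisation list, section 7.3.1 says: "This process will ensure there can be no allocation bias".

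**What is recorded at entry.** Section 7.5 opens with "Baseline data will be collected to describe the trial population (so that comparisons can be made with other populations" and lists age, sex, ethnicity, diagnosis, site of care, home country and type of consent. Section 10.3.1 repeats a shorter list. Table 3 ticks demographics and medication at entry, but fluid intake and Nu-DESC only during the trial. Delirium before entry is handled by exclusion (g), "patient has had delirium in last 24 hours". The primary model in section 10.3.2 adjusts for home country, unit type, disease category, age and sex.

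**The concern.** Cluster randomisation balances sites. The participants within those sites are comparable only if the same kinds of patient can enter in both arms. Here a rule of entry refers to the arm, and it is applied by staff who know the arm. If patients already on CAH enter at B sites and are turned away at A sites, arm B gains a group with no counterpart in arm A. Any difference in that group's underlying risk of delirium, or in its survival, would be read as an effect of CAH. Because neither prior CAH nor a Nu-DESC score is planned at entry, the trial report would have no baseline row in which the imbalance could appear, and no covariate with which to adjust for it.

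**Working it through.** **1. Eligibility by type of patient, other criteria met**

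| Patient at screening | B site | A site |
|---|---|---|
| Not on CAH | Eligible | Eligible |
| On CAH because it is the site's allocated standard | Eligible (6.2) | Counterpart is the same kind of patient, not on CAH: eligible |
| On CAH for another reason, e.g. begun before admission | Eligible (6.2) | Not stated. Exclusion (c) and a package without CAH (8.1) point to leaving the patient out |

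Only the third row can unbalance the arms. It also shows a tension within 6.2: exclusion (c) is printed for both arms, yet the B sentence admits patients on CAH and mentions only the inclusion criteria as a condition.

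**2. What the planned data could show**

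- Baseline list (7.5, 10.3.1): no prior CAH, no Nu-DESC.
- Table 3, entry column: medication is ticked, but section 8.4 says the fluid is not regarded as a drug, so that item need not capture CAH.
- Fluid intake during the trial: in arm B this does not separate CAH begun before entry from trial CAH.
- Per-protocol analysis (10.3.2): concerns compliance with fluids, not status at entry.

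**3. The plan's sample size, reproduced as a base**

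Inputs from section 10.1: 60% against 50%, power 90%. Alpha is taken as two-sided 0.05, as in section 10.3.2; the 0.5 printed in 10.1 does not reproduce the figure.

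- n per arm = [1.96√(2 × 0.55 × 0.45) + 1.2816√(0.60 × 0.40 + 0.50 × 0.50)]² / 0.10² = (1.379 + 0.897)² / 0.01, about 518.1, so 519 per arm and **1038** in total, as stated.
- Design effect 1 + 19 × 0.025 = 1.475. 1038 × 1.475 = 1531. With 5% attrition this is 1531/0.95 = 1612, or 1531 × 1.05 = 1608, close to the stated 1600.
- Effective n per arm at 1600: 1600 × 0.95 / 1.475 / 2 = 515, giving power 0.898.

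Nothing in this calculation allows for a difference between arms in who is eligible.

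**4. Illustration under assumptions**

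Let f be the share of arm B in the third row of the table in step 1, with none in arm A, and d the difference in their underlying delirium risk from other participants. Bias in the risk difference = f × d. The protocol gives neither f nor d. For f I borrow figures on CAH use from the protocol's background: 12% (low end of the cited range for cancer patients in the last week of life, section 1), 29% (at death, 2013 audit) and 43% (last 24 hours, 2016 audit: "43% patients were receiving CAH", section 2). None of these is a share of trial entrants. The values of d (5, 10, 20 points) are mine.

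- Type I error, no true effect and bias b favouring CAH: Φ(b/SE − 1.96) + Φ(−b/SE − 1.96), with SE = √[(0.24 + p(1 − p))/515] and p = 0.60 − b.
- Power, true 10-point effect and bias against CAH: two-proportion power at 515 per arm for 0.60 against 0.50 + b.

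| f | d (points) | Bias (points) | Type I error | Power |
|---|---|---|---|---|
| 12% | 5 | 0.6 | 0.054 | 0.86 |
| 12% | 20 | 2.4 | 0.123 | 0.69 |
| 29% | 10 | 2.9 | 0.157 | 0.63 |
| 43% | 10 | 4.3 | 0.288 | 0.46 |
| 43% | 20 | 8.6 | 0.797 | 0.07 |

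Worked row, f = 29% and d = 10: b = 0.029, SE = √[(0.24 + 0.571 × 0.429)/515] = 0.0307, b/SE = 0.945, and Φ(−1.015) + Φ(−2.905) = 0.155 + 0.002 = 0.157.

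These figures are on the risk-difference scale; the planned model is logistic. They show that the outcome runs from negligible to serious depending on two unknowns.

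**The case against.** The best defence is that the B sentence follows from the design. CAH is the allocated standard at B sites, and section 7.2 seeks consent for use of data, not for treatment. A B-site patient may therefore be on CAH, because of the allocation, before anyone asks for consent. Without the sentence arm B would lose such patients while arm A kept their counterparts. This stands. It confines the problem to patients on CAH for other reasons. It also rules out one obvious remedy: restricting both arms to participants not on CAH at entry would condition on something that follows from allocation, and could add bias.

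Several stronger readings are tempting and are not supported.

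- A reader might infer that the arms do recruit different populations. The text is silent on A sites, and exclusion there is an inference from (c) and from the content of intervention A. The silence is the defect.
- A reader might infer that an imbalance could never be detected. Screening logs record the reason for ineligibility (7.1), and clinical notes and drug charts are source documents (7.6), so partial reconstruction is possible. The protocol does not plan it.
- A reader might take the sentence in 7.3.1 as a false claim about participants. It follows a description of matching sites to a list and concerns sites only. The risk is that it is read more widely.
- A reader might suppose that arm B sheds patients who tolerate CAH poorly. Contraindications to CAH and to cannulation, and dehydration, are exclusions in both arms.

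The missing entry Nu-DESC is partly offset by exclusion (g), which narrows the range of any entry score, and by four-hourly scoring afterwards, although the first such score may follow the start of trial CAH. Finally, 43% is a hospital figure for the last day of life, whereas section 2 expects mainly inpatient hospices, so it is an upper case.

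**Conclusion.** The point holds as follows. Section 6.2 states eligibility of patients already on CAH by allocated arm and leaves A sites without a rule. Unblinded teams apply it after site allocation. No planned baseline item would let the resulting difference be assessed or adjusted for. That is more than missing detail, because staff who follow the text as written can select different patients in the two arms.

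The size and the direction of any bias cannot be derived from the protocol. The range of 0.6 to 8.6 points rests on assumed values of f and d and on no such patients entering arm A. It would shrink if A sites also admit them, or if most pre-entry CAH at B sites stems from the allocation. The case for acting rests on the wording and the missing entry record, not on any single figure in that range.

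**What to change.** 1. **Section 6.2:** reconcile the B-site sentence with exclusion (c) in one statement on CAH before entry that applies in the same way in both arms. Its clinical content is for the protocol team.
2. **Table 3 (entry column) and section 7.5:** add CAH status before entry, with start time and whether it was begun before admission or as the site's allocated standard; and one Nu-DESC score taken at entry.
3. **Reporting:** show both items by arm, together with screening-log exclusions for CAH by arm.
4. **Analysis:** add a supportive analysis of the primary outcome adjusted for entry Nu-DESC. It should stay supportive, since at B sites the entry score may follow CAH given because of the allocation. Any sensitivity analysis on prior CAH should concern only CAH not started because of the site's allocation.
5. **Section 7.3.1:** limit the sentence on allocation bias to the allocation of sites.

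The cost is a short amendment and two entry items, one of which staff already score every four hours. A common rule might slow recruitment slightly in one arm.

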7 TRIAL PROCEDURES

7.1 Recruitment

Participants will be inpatients at the trial sites and will need to meet all of the inclusion criteria, and not meet any of the exclusion criteria of the trial (see above). [All patients that meet the inclusion/exclusion criteria for the trial will be eligible for the trial].

The clinical team will identify suitable patients as part of routine clinical practice, and the research team will then approach the patient, personal consultee or nominated consultee (as appropriate) to see whether they want to take part in the trial.

Each trial site will have a screening log, which records anonymised personal data for all screened patients (i.e., initials and date of birth), this information will be obtained from the patient's medical records. Information will also be recorded about reasons for non-participation, e.g., patient ineligible (reason stated), patient declined, personal / nominated consultee declined, other reason (reason stated): this information will be provided by the clinical team / research team (as appropriate).

Separate information sheets have been developed for participants, personal consultees, and nominated consultees. Similarly, separate consent forms have been developed for participants, personal consultees, and nominated consultees.

Trial sites will be required to develop a Cluster Representation Mechanism (CRM) to represent the interests of the cluster (and the individuals within the cluster) [30]. The CRM has the same rights as an individual participant in a normal randomised trial; the CRM has the right to withdraw the cluster from the trial if it decides that the trial is no longer in the interests of the cluster. The CRM includes a Study Gatekeeper (who is responsible for cluster as a whole, permits the cluster taking part in the trial, and monitors the continued involvement of the cluster in the trial, e.g., senior clinician), and a Trial Guardian (who is responsible for the individuals in the cluster, permits individuals to take part in the trial, and monitors the continued involvement of individuals in the trial, e.g., senior nurse). The CRM will be independent of the research team and will work to a formal document that describes the role of the CRM.

7.2.1 Additional consent provisions for use of participant data in ancillary studies

In addition to providing consent for the use of the collected clinical information in this trial, the participants or personal / nominated consultees will be asked to provide consent for the potential use of the collected clinical information (anonymised) in future studies. [Enrolment to the trial is not dependent on consent for the potential use of the collected clinical information in future studies].

7.3 The randomisation scheme

Randomisation will be undertaken 1:1 by site (cluster), to ensure balance and equal numbers in each intervention group, stratifying by home country (i.e., England, Wales, Scotland or Northern Ireland), and by type of unit (i.e., hospital or hospice). Randomisation will be undertaken by the Trial Statistician at Surrey CTU, using a blocked randomisation with separate blocks (of random length) assigned to hospitals and hospice groups within each of the home countries to ensure balance on these factors.

7.3.1 Method of implementing the randomisation/allocation sequence

A sampling frame containing all approved sites, categorised by type of unit and home country will be drawn up, and each unit matched to an allocation from the independently prepared randomisation list by the Trial Statistician. This process will ensure there can be no allocation bias.

7.4 Blinding

The trial is unblinded (to participants and researchers).

[figure not shown]

Figure 2 – Consent flow chart.

7.5 Baseline data

Baseline data will be collected to describe the trial population (so that comparisons can be made with other populations):

- a) Age
- b) Sex – female, male

- c) Ethnicity
- d) Primary diagnosis – cancer, non-malignant (with specific diagnosis)
- e) Site of care – hospital, hospice
- f) Home-country – England, Northern Ireland, Scotland, Wales
- g) Type of consent – participant, personal consultee, nominated consultee

7.6 Trial assessments

The trial lasts for 14 days (maximum). However, it is expected that the majority of participants will have died within this time period (of their primary disease).

Participants will be reviewed every four hours during the trial by the clinical team, and the following assessments completed (by the clinical team):

- ❖ Nu-DESC score (see above)
- ❖ m-RASS score (see above)
- ❖ Presence of audible upper airway secretions (“death rattle”)
- ❖ Presence of pain – patient reported
- ❖ Presence of shortness of breath – patient reported
- ❖ Presence of nausea and vomiting – patient reported (nausea and vomiting), or nurse assessment (vomiting)
- ❖ Presence of adverse effects of CAH (see above)

The clinical team will also record the participant's fluid intake (oral, CAH), and medications / other interventions provided to the participant (and the indications) during the trial.

Data on usage of CAH paraphernalia (e.g., cannulae, giving sets), and paraphernalia relating to other interventions will also be recorded (to support the health economic analysis).

Overall survival (from the time of randomisation) will be recorded. [Participants that survive >14 days will continue to be followed up in order to determine their date of death].

The clinical team will complete a trial-specific clinical observation document, which will be transcribed by the research team into the case report form (CRF). The research team will also use the participant's clinical notes and drug charts as source documents.

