8 TRIAL TREATMENTS

The health technology being assessed is clinically-assisted hydration (CAH), i.e., parenteral fluids (intravenous/subcutaneous fluids). Currently, there is no agreed “standard of care”, with some patients receiving CAH during the last days of life, whilst other patients do not receive CAH during the last days of life (but receive oral fluids, and/or regular “mouth care”). Moreover, some patients have CAH withdrawn during the last days of life.

Research sites will be randomised to either “standard intervention A” or “standard intervention B” (see below), and this will become the standard of care at the research site for the duration of this trial. The interventions represent the current typical standards of care in the UK.

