10.2 Planned recruitment rate

Recruitment will take place over 24 months, which will require an overall recruitment rate of 67 per month (which is < 1 participant per centre/month assuming centres can be quickly opened).

The “green” criteria for progression from internal pilot to full trial at 12 months (see below) are entirely realistic based on the recruitment rate in the feasibility trial.

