10.3.3 Secondary outcome analysis

Secondary outcomes will be handled similarly for dichotomous outcomes, including at the various thresholds for delirium on the NUDESC scale (≥ 1 versus ≥ 2). Survival and time to delirium will be assessed by Kaplan Meier plot and analysed using a Cox regression model. Where there are problems of convergence in models using random effects, centre will be

converted to a fixed effect. Intervention tolerability and adherence to the CAH procedures will be presented. Exploratory analysis (to be detailed in the SAP) will include methods accounting for the repeated observations on outcomes.

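### Overall survival is timed from randomisation, but only sites are randomised, so section 7.6 gives participants an origin that none of them has

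*Protocol*

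**What the plan says.** Section 7.6 of the protocol fixes the origin for survival: "Overall survival (from the time of randomisation) will be recorded".

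The unit of randomisation is the site throughout. Section 4 describes a cluster trial "where the research sites are randomised to one or other intervention". Section 7.3 says "Randomisation will be undertaken 1:1 by site (cluster"), and section 7.3.1 sets out the mechanism: "A sampling frame containing all approved sites, categorised by type of unit and home country will be drawn up", with "each unit matched to an allocation from the independently prepared randomisation list". Section 8 adds that the allocated intervention is then fixed: "this will become the standard of care at the research site for the duration of this trial". No section describes a participant-level randomisation step.

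Survival is a listed secondary objective (section 3) and endpoint (section 3.2), and section 3.2 gives no origin for it. Section 10.3.3 plans the analysis, again without an origin: "Survival and time to delirium will be assessed by Kaplan Meier plot", followed by a Cox model.

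Other parts of the protocol do use participant-level starting points. Adverse event recording begins at consent (section 9.3). Costs are counted from trial entry, and the cost-effectiveness measure from recruitment (section 10.10).

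**The concern.** The only randomisation date in this trial belongs to the site. Read as written, each participant's survival time would include the interval from the site's allocation to that person's enrolment. Nobody can die as a participant during that interval. Its length depends on when the site was allocated, when it opened and how fast it recruited, none of which is survival.

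The rationale (section 2) cites guidance that it is uncertain whether clinically-assisted hydration (CAH) prolongs life or whether withholding it hastens death. Survival is the endpoint that addresses this question. Participants have a prognosis of a week or less, so even a modest administrative lag would be much longer than the quantity of interest.

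This is not a detail left to the SAP: the protocol states the origin, and states one that participants do not have.

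**Working it through.** **Inputs from the protocol**
- 1600 participants, 80 centres, 20 per centre (section 10.1).
- Recruitment over 24 months (section 10.2): "Recruitment will take place over 24 months, which will require an overall recruitment rate of 67 per month".
- Internal pilot thresholds for recruitment per site per month (section 10.6, Table 5): green at 4 or more, red below 2.
- Prognosis at entry of a week or less (section 6.1), taken as 7 days.

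**Assumptions, because the protocol gives no site allocation dates**
- Each site is allocated when it opens. Any set-up delay after allocation would lengthen the lag.
- Each site accrues its 20 participants evenly.
- A month is 30.4 days.

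**Step 1. Reproduce the planned rate.** 1600 / 24 = 66.7 per month, which matches the stated 67. Per centre, 66.7 / 80 = 0.83 per month, which matches the statement that it is below 1.

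**Step 2. Lag from site allocation to entry.** The accrual window is W = 20 / rate, and the mean lag under even accrual is W / 2. The lag's share of mean measured time is lag / (lag + 7 days).

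| Rate per site per month | Window W | Mean lag | Lag as share of measured time |
|---|---|---|---|
| 0.83 (section 10.2) | 24 months | 12 months (365 days) | 365 / 372 = 98% |
| 2 (red threshold) | 10 months | 5 months (152 days) | 152 / 159 = 96% |
| 4 (green threshold) | 5 months | 2.5 months (76 days) | 76 / 83 = 92% |

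These are means. Under the same model, a site's first participant enters on average about 1.1 months after allocation with a 24-month window, and about 0.14 months (some 4 days) with a 3-month window.

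**Step 3. Effect on the Cox model when lags are balanced.** This is a simulated illustration: 800 per arm, exponential survival from entry, assumed median 4 days in the control arm, true hazard ratio 0.80, lag uniform over the window in both arms, no clustering, 20 replicates per setting. With the clock started at entry, the mean estimate is about 0.80 (0.79 to 0.80 across settings). With the clock started at site allocation:

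| Accrual window | Estimated hazard ratio |
|---|---|
| 3 months | 0.90 |
| 5 months | 0.96 |
| 10 months | 0.99 |
| 24 months | 1.00 |

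The 3-month row is faster than any rate named in the protocol (20 / 3 = 6.7 per site per month) and is shown as a lower bound.

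**Step 4. Effect of unbalanced lags.** The set-up is the same, with a 12-month window and no treatment effect. A difference between arms in lag of 0, 15 or 30 days gives hazard ratios of about 1.01, 0.83 and 0.70. The 15- and 30-day figures are illustrative inputs, not protocol values.

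**The case against.** The strongest reply is that nobody would apply the sentence literally. The next sentence of section 7.6 concerns people who survive beyond 14 days, and that limit can only run from participant entry. Section 7.12 ends participation on the same clock. Section 3.2 takes survival from the clinical observation document, which is kept per participant, and nothing says that it holds the site's allocation date. The phrase looks like wording carried over from an individually randomised trial.

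That reading of the intention is probably right, and it limits the practical risk. It does not settle the text. The protocol never says which participant event replaces randomisation: consent, consultee agreement or first infusion, for example. When survival is measured in days, the choice matters, and first infusion is not part of Standard intervention A.

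A reader might also infer stronger things that the documents do not support:
- *The clock starts months early for everyone.* The lag is inferred, and the first participants at a site could enter within days or weeks of allocation.
- *More than 95% of measured time is always artefact.* At the protocol's own green rate the share is about 92%.
- *The analysis would compare recruitment timing instead of survival.* Sites are allocated 1:1 within country and unit type, and nothing in the protocol gives reason to expect the lag to differ between arms. The expected harm is therefore mainly dilution. A spurious difference needs an imbalance in lag.
- *Every time-to-event endpoint is wrongly defined.* Only survival carries a stated origin. For the others the origin is left open, which the SAP may properly settle.

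**Conclusion.** The point holds as an error in the stated definition of a secondary endpoint. Section 7.6 ties survival to an event that happens to sites and not to participants, and no other section corrects it. If followed, it would add a mean of about 2.5 to 12 months to survival times of about a week or less, and would pull a true hazard ratio of 0.80 to about 0.96 to 1.00. The lag rests on allocation at site opening and even accrual of 20 per site. The hazard ratios rest also on an assumed 4-day median, exponential survival and balanced lags. The contradiction itself needs none of these assumptions. It should be corrected before the survival analysis is specified in detail.

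**What to change.** In section 7.6, replace the bracketed origin with: from the date and time of participant entry to the trial (consent or consultee agreement), defined identically in both arms. This agrees with the participant-level starting points already used in sections 9.3 and 10.10.

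The cost is a one-line amendment. The consent form is already signed and dated (section 13.4), so the date exists. If the clock time of entry is not already captured, it needs one field on the case report form. Design, sample size and primary analysis do not change.
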